6.3 Randomization Procedure

This is a single-arm, open-label study in which subjects serve as their own controls. No randomization was performed.

6.4 Efficacy Measures

The primary efficacy measure is the number of FI episodes as measured on a 2-week bowel diary.

A subject is classified as a treatment responder if she has a \geq 50% reduction in the average number of FI episodes per week, as compared to the baseline evaluation period.

Subject-reported outcomes related to symptoms and quality of life, as reported by the St. Mark's (Vaizey) Incontinence Severity Score and FIQOL, and the Patient Global Impression of Improvement (PGI-I) scores are also evaluated.

6.5 Safety Measures

Safety will be assessed using device-related adverse events and device-related serious adverse events. Adverse events will be adjudicated by a Clinical Events Committee (CEC). Please reference the CEC Charter ver. 2.0 for a detailed description of the adverse event adjudication process.

Page 9 of 19

Confidential

¹ Richter, et al. non-surgical management of stress urinary incontinence: ambulatory treatments for leakage associated with stress (ATLAS) trial. Clinical Trials 2007; 4: 92-101.

6.6 Pharmacokinetic Parameters

No pharmacokinetic parameters will be assessed.

6.7 Completion and Discontinuation

Subjects must complete at least 12 of the 14 consecutive days of the Baseline Diary and have documented at least 4 episodes of major or minor soiling (not staining) on their Baseline Diary. If either of these criteria is not met, or the subject is discontinued for any other reason prior to being fit with the Eclipse System, then the subject is categorized as a pre-fitting discontinuation, and a screen failure.

Eligible subjects then proceed with the Initial Fitting Visit. If a subject cannot obtain a suitable fit during this visit, and/or decides to withdraw, then the subject is categorized as a post-fitting discontinuation, and a screen failure.

Subjects who discontinue the trial after the Initial Fitting Visit, such as those who are deemed to not have a suitable fit during Fit Confirmation Visits or unsuccessful fittings on Repeat Fitting Visits, are also categorized as post-fitting discontinuations, and screen failures.

Subjects who achieve a successful fit but do not meet the Visit 4 Test Diary criteria (as described in protocol section 2.6.8), or who decide withdraw at or before Visit 4, are similarly categorized as post-fitting discontinuations, and screen failures.

Subjects who successfully meet the Visit 4 Test Diary criteria and successfully complete Visit 4 will enter the Treatment Period. These subjects are considered to be enrolled in the study, and any discontinuations after Visit 4 will be considered early terminations. The date of early termination and main reason for discontinuation will be recorded.

7 STUDY POPULATIONS

This study evaluates the durability of the efficacy and safety of the Eclipse System.

7.1 Subject Disposition and Visit Participation

All subjects who sign an informed consent will be classified as either screen failures (those who terminate prior to or at Visit 4, as defined in Section 6.7) or enrolled subjects.

7.2 Analysis Populations

The Safety Population will include all subjects exposed to any part of the Eclipse System during or after Visit 2 (Initial Fitting Visit). This will include all subjects who

were unsuccessfully fitted, and screen failures. This will be the primary analysis population for all safety analyses.

The Test Population will include all subjects who are successfully fit with the Eclipse Insert and successfully completed a Test Diary.

The Intent-to-Treat (ITT) Population will include all subjects who are successfully fit with the Eclipse Insert, successfully complete Visit 4, and enter the Treatment Period.

The Per-Protocol (PP) Population include all subjects in the ITT population who complete Visit 5, complete at least 10 out of 14 consecutive days of diary data at the 3 month visit, and have no major protocol deviations.

7.3 Protocol Deviations

All protocol deviations will be recorded on the appropriate case report form (CRF). Deviations will be categorized as: consent procedure not followed, eligibility criteria violation, subject diary deviation, study assessment not done, study assessment out of window, visit out of window, visit not done, or other.

All deviations will be reviewed by the sponsor, in conjunction with source documentation as necessary. Prior to database lock, the sponsor will determine which deviations meet the criteria for major protocol deviations.

All major protocol deviations may be summarized by deviation category. All deviations, both major and minor, may be listed by subject.

7.4 Subgroups

No analyses by subgroups will be performed.

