Clinical Investigational Plan

LIBERATE:

A Clinical Evaluation of the Eclipse™ System, a Vaginal Bowel Control (VBC) Therapy for Fecal Incontinence in Women

Protocol: CA005
Revision: D
Date: 09 Feb 2017

Study Sponsor:
Pelvalon, Inc.
[name]

LIBERATE Protocol Synopsis

Study Objective	To evaluate the durability of the safety and effectiveness of the Eclipse™ System after 3 and 12 months of use.
Study Design	Multi-center, prospective, within-subject control, open label clinical trial
Sites/ Subjects	Up to 150 treatment-eligible subjects may be enrolled into the 12 month Treatment Period at up to 15 clinical sites in the United States
Study Population	Adult females diagnosed with fecal incontinence (FI)
Study Duration	Screening Period: 5 - 7 weeks* Treatment Period: 12 months * Screening may be extended by up to an additional 6 weeks to allow for estrogen pre-treatment, if required
Primary Endpoint	The proportion of treatment responders, defined as a $\geq 50\%$ reduction in the average number of FI episodes per week, as compared to baseline, at the 3 month time point in the ITT population
Secondary Endpoints	
 1. Proportion of treatment responders at the 3, 6 and 12 month time points in the per protocol (PP) population 2. Change from baseline in mean scores on subject-reported outcomes related to symptoms and quality of life as reported by St. Mark's (Vaizey) Incontinence Severity Score, and FI Quality of Life (FIQOL) 3. Patient Global Impression of Improvement (PGI-I) scores at the 3, 6, 9 and 12 month time points
Safety Endpoint	Safety of the Eclipse System is assessed by the number of device-related (Eclipse System) adverse events, and device-related serious adverse events.
Subgroup Analyses	< 65 years of age versus ≥ 65 years of age
Inclusions: General Eligibility Criteria	
 1. Female sex 2. Age 19 years or older 3. History of FI for at least 6 months 4. Subject willing and able to give written informed consent to participate in the study 5. Subject can read, write and communicate fluently in English (the study diaries, questionnaires and instructions are only provided in English) 6. Subject willing and able to comply with visit schedule 7. Subject is able to physically manage the insertion and removal of the Insert¹

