3.9 Subgroup Analyses

The primary and secondary analyses will be repeated on the subgroups of < 65 years of age and ≥ 65 years of age.

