- Average number of solid stool BMs per week: 7 * (# BMs with Bristol stool scale score of 1 5) / (# days of diary entry)
- Average number of BM days per week: 7 * (# days with ≥1 BM) / (# days of diary entry)
- Average number of episodes per week: 7 * (# episodes) / (# days of diary entry). Episodes include both BM episodes (normal, minor FI, and major FI) and staining episodes.

- Average proportion of episode type: (# episodes of that type) / (# total episodes), where episodes includes both BM episodes and staining episodes
- Average Bristol score: (sum of Bristol scores) / (# BMs)
- Average proportion of loose stools: (# BMs with Bristol stool scale score of 6 or 7) / (# BMs)
- Average proportion of solid stools: (# BMs with Bristol stool scale score of 1 5) / (# BMs)

Treatment response is defined as having a ≥50% reduction in the average number of FI episodes per week on the Treatment Diary (3, 6, or 12 months) as compared to the associated Baseline diary.

Subjects are classified into **FI phenotypes** based on the results of the FIQOL at Baseline. Subjects ranking question 2k, "I can't hold my bowel movement long enough to get to the bathroom", as more severe than question 2l, "I leak stool without even knowing it", are classified as *urge-predominant*. Those ranking question 2l as more severe than question 2k are classified as *passive-predominant*. Those ranking both questions the same, when the result is "most of the time" or "some of the time", are classified as *both* predominances. Those ranking both questions as "a little of the time", "none of the time", or "N/A" will not be categorized as having an FI phenotype.

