9 DEMOGRAPHICS AND BASELINE CHARACTERISTICS

All summaries of demographic information will be based on the ITT population.

Demographic information, including age (calculated as the difference between date of informed consent and birthdate, in years), body mass index (BMI), and race/ethnicity, will be summarized. The number and percentage of subjects <65 years of age and ≥ 65 years of age will also be presented.

Medical history such as types of previous urogenital surgeries, current or recent sexual activity, parity, menopause status, Digital Rectal Examination Scoring System (DRESS) resting and squeeze scores, and comorbidities will also be summarized.

Baseline FI characteristics such as FI type, duration of symptoms, previous treatments, self-management, and etiology will also be summarized.

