10 CHANGES IN CONDUCT OR PLANNED ANALYSES FROM THE PROTOCOL

This analysis plan was developed in conjunction with CA005 Protocol Revision D, dated 09 Feb 2017. No changes in conduct or planned analysis have occurred.

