11.4 Exploratory Analyses

No exploratory analyses are planned.

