11.5 Subgroup Analyses

Subgroup analyses may be performed by FI phenotype, including but not limited to analyses of FI episodes, FIQOL, St. Mark's (Vaizey), and demgraphic comparisons.

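### The SAP rules out the age-group analyses that the protocol commits to, contradicts itself on subgroups, and wrongly states that no planned analysis changed from Protocol Revision D

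*SAP*

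**What the plan says.** **Age groups.** The synopsis of Protocol Revision D names one subgroup comparison, women under "65 years of age versus ≥ 65 years of age". Protocol 3.9 makes it a commitment: "The primary and secondary analyses will be repeated on the subgroups of" those under 65 and those 65 or older. SAP 7.4 says "No analyses by subgroups will be performed". The age cut appears elsewhere in the SAP only in section 9, for baseline description: "The number and percentage of subjects <65 years of age and ≥ 65 years of age will also be presented".

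**Phenotype groups.** SAP 8.3 sorts subjects into urge-predominant, passive-predominant or both, "based on the results of the FIQOL at Baseline". SAP 11.5 then says: "Subgroup analyses may be performed by FI phenotype, including but not limited to analyses of FI episodes, FIQOL, St. Mark's (Vaizey), and demgraphic comparisons". The protocol plans no analysis by phenotype. SAP 11.4 says "No exploratory analyses are planned".

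**Disclosure.** SAP 10 ties the plan to Protocol Revision D of 09 Feb 2017 and says "No changes in conduct or planned analysis have occurred".

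**The concern.** A programmer who follows SAP 7.4 will not produce analyses that the protocol says will be done. A programmer who follows SAP 11.5 may produce subgroup analyses that 7.4 forbids and the protocol does not mention. SAP 10 is where a reader would look to learn of such departures, and it denies that there are any.

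The trial is single-arm and open-label, so much of its credibility rests on doing and reporting what was written down beforehand. A committed subgroup analysis disappears, an optional one takes its place, and neither change is declared. A later reader then cannot tell which subgroup results were planned. Once SAP 10 is seen to be wrong on this point, its silence on other points gives no assurance either.

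**Working it through.** **1. Planned analyses side by side**

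| Item | Protocol Rev D | SAP | Declared in SAP 10? |
|---|---|---|---|
| Age groups | Primary and secondary analyses repeated (synopsis, 3.9) | None (7.4); baseline count only (9) | No |
| FI phenotype | Not planned | Optional (8.3, 11.5), against 7.4 | No |
| PP diary rule | At least 10 of 14 days at each time point (3.3) | At least 10 of 14 days at 3 months (7.2); later missing diaries excluded from the responder analysis at that time point (8.2, 11.2.1) | No |
| Responder analysis at 6 and 12 months | PP only (3.5, 3.7) | ITT added to PP (11.2.1) | No |
| FI days per week, change and percent change | At 3, 6 and 12 months (3.8) | Measure derived (8.3), not listed in 11.3 | No |

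The first two rows show that 7.4 conflicts with both the protocol and SAP 11.5. Any one row is enough to make the SAP 10 statement untrue.

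**2. Populations left open.** Protocol 3.7 places the FIQOL and St. Mark's changes on the PP population. SAP 11.2.3 names PP for the FIQOL summaries but no population for the repeated-measures model. SAP 11.2.4 names PP for the bother scale but no population for the severity score. SAP 11 makes ITT the primary population for efficacy, with PP supportive where specified. The text therefore supports either population for these two items.

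**3. Count of affected results.** Per age group, protocol 3.9 with 3.5 and 3.7 gives:
- primary responder proportion: 1
- PP responder proportion at 3, 6 and 12 months: 3
- St. Mark's at 3, 6, 9 and 12 months: 4
- FIQOL, 4 subscales × 4 visits: 16
- PGI-I at 3, 6, 9 and 12 months: 4

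The total is 1 + 3 + 4 + 16 + 4 = 28, and 28 × 2 groups = 56. For FI days, 2 measures × 3 time points = 6. These are counts of table entries and do not measure consequence.

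**4. Size of the PP difference.** The inputs come from protocol 3.11: dropout of 21.3% by 3 months and 33% by 12 months, and an ITT set of 40 to 150. The plan's own completer figures come first: 150 × (1 − 0.33) = 100.5 and 40 × 0.67 = 26.8, against the stated range of approximately 25 to 100. The 3-month PP set, before removing major deviations and missed diaries, is then:
- SAP 7.2: 150 × (1 − 0.213) = 118.1; 40 × 0.787 = 31.5.
- Protocol 3.3 read literally, with diaries needed at 3, 6 and 12 months: 100.5; 26.8.
- Difference: 118.1 − 100.5 = 17.6; 31.5 − 26.8 = 4.7.
- Protocol 3.3 read separately for each time point: difference 0.

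**5. Primary test.** It uses the whole ITT set at 3 months, and nothing above changes its data or rule. The stated power also reproduces. The assumed response rate is 0.856 × (1 − 0.213) = 0.674, given as 67%. At n = 40 the exact test needs 23 responders (one-sided alpha 0.0189) and has power 0.924, consistent with the stated 90% or more.

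**The case against.** The strongest reply is that little hangs on this. SAP 8.1 makes every p-value outside the primary endpoint descriptive. Revision D also dropped age-balanced recruitment, so the age groups may be small. The documents give no age split. If a group had 10, 20 or 75 women, the primary test within it would have power 0.31, 0.67 or 0.998 at a 67% response rate. A SAP may refine a protocol. All of this stands. It supports descriptive reporting by age, or a reasoned removal, but not silence: the current synopsis and 3.9 still carry the commitment, and SAP 10 denies any change.

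It could be argued that the open wording of 11.5 covers age. It does not, because that wording widens the outcomes analysed by phenotype and adds no other grouping.

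Several stronger readings are tempting, and the documents do not support them:
- **SAP 11.4 as a further direct contradiction.** It does not mention subgroups, and 11.5 is optional where 11.4 speaks of what is planned. The tension is indirect: the phenotype analyses are exploratory in substance and carry no label.
- **St. Mark's severity moved to ITT.** That is one reading of the SAP 11 default. It would apply equally to the FIQOL model, and a simple omission explains both. What is established is that the populations are not stated.
- **FI days abandoned.** SAP 8.3 derives the measure, and SAP 8.1 says how continuous data are summarised. What is missing is a line in 11.3.
- **A PP set known to differ by 18 subjects.** That holds only under the literal reading of protocol 3.3. By 12 months the responder gap largely closes, because SAP 8.2 and 11.2.1 exclude missing diaries.
- **The 6- and 12-month ITT analyses as a harm.** They count missing diaries as non-response, so they are a conservative addition that needs disclosure only.

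**Conclusion.** The point holds on the current text of both documents. SAP 7.4 removes analyses that protocol 3.9 and the synopsis commit to, SAP 11.5 contradicts 7.4, and SAP 10 is untrue for the five items tabulated. The FIQOL model and the St. Mark's severity score also lack a stated population and must be reconciled with protocol 3.7.

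The consequence is moderate. As the SAP stands, 56 age-group results have no provision and 6 FI-days results have no explicit line. The 3-month PP difference runs from zero to about 18 of 150 (5 of 40). The upper figures assume the literal reading of protocol 3.3 and the planned dropout rates, with major deviations and missed diaries ignored. No effect on any response rate has been shown.

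A reader might infer that the primary conclusion is at risk, or that analyses were dropped in order to report selectively. The documents support neither. The primary test is untouched, and the text shows inconsistency without showing its reason.

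**What to change.** 1. Replace SAP 7.4 with the protocol 3.9 analyses by age group, reported as descriptive estimates: the 3-month ITT responder proportion with its exact interval, and the secondary endpoints. Alternatively, state and justify their removal in SAP 10; the end of age-balanced recruitment could be cited there. Either route resolves the contradiction.
2. Make 7.4 and 11.5 agree. Label the phenotype analyses exploratory and not in the protocol, and word 11.4 to match.
3. Add change and percent change in FI days per week at 3, 6 and 12 months to 11.3, or declare the removal.
4. State the analysis population for the FIQOL model in 11.2.3 and for the St. Mark's severity score in 11.2.4.
5. Rewrite SAP 10 to list every departure from Revision D: the age analyses if dropped, the phenotype subgroups, the PP definition together with the time-point rule in 8.2 and 11.2.1, the added ITT responder analyses, the FI-days analysis if dropped, and the FIQOL or St. Mark's population if it is not PP.

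The cost is a few sentences in SAP 7.4, 10, 11.2.3, 11.2.4, 11.3, 11.4 and 11.5, a rerun of existing efficacy tables by age group (56 results), and one FI-days table (6 results). No new data are needed: age and diaries are already collected, and SAP 9 already tabulates both age groups.

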8 STATISTICAL ANALYSIS

8.1 General Considerations

Continuous data will be summarized using count (n) the number of non-missing values and mean, median, standard deviation, minimum and maximum as appropriate. The interquartile range (IQR) may also be reported as appropriate. Categorical data will be summarized using counts and frequencies. In general, means and medians will be presented to 1 more decimal place than collected, and standard deviations to 2 more decimal places. Where appropriate, p values will be presented to 4 decimal places.

A one-sided, 2.5% significance level will be used for the primary efficacy endpoint. All p-values, aside from those in the primary efficacy endpoint, are presented for descriptive purposes only. No adjustments will be made for multiple comparisons.

Recorded data may be presented in data listings, aside from cost utilization data which is evaluated under a separate analysis plan. If listed, enrolled subjects will be listed first, followed by screen failures, where appropriate.

8.2 Handling of Missing Data

Subjects are required to complete at least 12 of 14 consecutive days in the Baseline and Test Diaries. If any subject arrives at a 3, 6, or 12 month visit with less than 10 days of completed diary data, they will be given one opportunity to reschedule the follow up visit as soon as possible within the next two weeks while completing a new Treatment Diary for the remainder of the required 14 consecutive day diary period.

Any such partially completed diary information (that does not have additional days completed to total at least 10 of 14 consecutive days) will be listed but summary measures (average FI episodes per week, etc.) will not be calculated. If data is provided for more than 14 days, data from the first 14 consecutive days which has at least 10 days completed will be analyzed.

Missing item results for the FIQOL or St. Mark's (Vaizey) Incontinence Severity score will be handled as described in Sections 11.2.3 and 11.2.4, respectively.

Analyses of treatment response (defined in Section 8.3) utilizing the ITT population, including but not limited to the primary analysis, will classify subjects who do not complete the diary (either partially completed, not completed, or discontinued study prior to that time point) as non-responders for that time point.

No imputation of treatment response will be performed for analyses utilizing the Per-Protocol population (i.e., subjects who do not complete the diary are excluded from analysis).

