2.7 Treatment Period

Subjects who enter the Treatment Period will return for scheduled visits at 3, 6, 9, and 12 months after Visit 4. All eligible subjects will complete a 2-week Treatment Diary during the last 2 weeks prior to the 3, 6 and 12 month visits. There is no Treatment Diary required at the 9 month visit. Subjects will be instructed to complete the diary for 14 consecutive days while wearing the Eclipse Insert. The timing of the start and/or completion of the Treatment Diary may be adjusted by up to 2 weeks (without being considered a protocol deviation) if a subject's menstrual cycle interrupts their wearing of the Eclipse Insert during the two-weeks when the Treatment Diary is scheduled, rendering assessment of effectiveness during this period of time inappropriate.

In addition, subjects will be allowed to repeat (stop and restart) their Treatment Diary if the two weeks recorded were unusual or unrepresentative of their true condition due to circumstances outside of their control e.g. illness, injury, natural catastrophe, or family emergency. Only the repeat diary data will be data entered. Both original and repeat diaries must be retained. Pelvalon should be notified immediately and the rationale for allowing a subject to repeat their diary provided. The case will be evaluated by the Executive Committee, and a documented written approval must be obtained prior to using the repeat diary for data entry.

If any subject arrives at a 3, 6, or 12 month visit with less than 10 days of completed diary data, they will be given one opportunity to reschedule the follow up visit as soon as possible within the next two weeks while completing a new Treatment Diary for the remainder of the required 14 consecutive day diary period. After the second attempt, any non-completed diary will be treated as missing data.

The subject will undergo a pelvic exam at each visit in order to verify proper use of the Eclipse Insert and adequate hygiene, as well as to assess any adverse events.

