Treatment-eligible Subject (Enrolled): A subject who successfully completes the Screening Period and enters the Treatment period is considered enrolled. This is defined as a subject having a confirmed successful fitting (as determined at Visit 3), having recorded a minimum of 12 out of 14 consecutive days of diary data after a successful fitting (i.e. on their Test Diary), and having demonstrated at least a 50% reduction in the average number of FI episodes in the Test Diary at Visit 4 as compared to the Baseline Diary.

Treatment Responder: An enrolled subject who demonstrates at least a 50% reduction in the average number of FI episodes per week on her Treatment Diary compared to her Baseline Diary is a responder for that time period. An enrolled subject must also have at least 10 out of 14 consecutive days of recorded diary data on her Treatment Diary to be defined as a responder for that time period.

Treatment Non-Responder: An enrolled subject who does not demonstrate at least a 50% reduction in the average number of FI episodes per week on her Treatment Diary compared to her Baseline Diary, is a non-responder for that time period. An enrolled subject with less than 10 out of 14

consecutive days of recorded diary data on her Treatment Diary will also be classified as a non-responder for that time period.

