8.3 Definitions

Baseline measurements are the last recorded values for each parameter prior to the Initial Fitting Visit. Baseline diary measurements, such as average numbers of FI episodes, are based on the entire Baseline Diary. Other assessments are typically recorded at Visit 1.

Change from baseline is calculated as result – (baseline result).

Percent change from baseline is calculated as 100^* (change from baseline) / (baseline result). This statistic is represented in tables by % Δ .

Study day is calculated as date – Visit 4 date, for visits occurring prior to Visit 4 (the beginning of the Treatment Period), and calculated as date – Visit 4 date + 1, for visits on or after Visit 4. Study day will not be presented for screen failures.

All calculations based on diary data will be calculated based on the entire reported diary period, if the diary was completed for that time period (12+ days for Baseline and Test diary, 10+ days for 3, 6, and 12 month diaries as per Section 8.2). If >14 days were completed for any time period, only the first 14 days will be used for computations. If a diary was repeated as allowed per protocol or Sponsor-approved Protocol Deviation, the calculations will be performed on the repeat diary information only.

A **bowel movement (BM)** is defined as any passing of stool reported as a "normal (continent) BM", "minor soil" or "major soil". Staining episodes will be omitted from this definition.

A fecal incontinence (FI) episode is defined as any passing of stool reported as a "minor soil" or "major soil". Staining episodes will be omitted from this definition.

Loose stool is defined as a BM with a Bristol stool score of 6 or 7. **Solid stool** will be defined as a BM with a Bristol stool score of 1-5.

The following statistics will be calculated from diary data, for each diary period:

- Average number of FI episodes per week: 7 * (# episodes) / (# days of diary entry)
- Average number of FI episodes while insert in place, per week: 7 * (# episodes while insert is in place) / (# days of diary entry)
- Average number of FI days per week: 7 * (# days with ≥1 FI episode) / (# days of diary entry)
- Average number of urgent BMs per week: 7 * (# urgent BMs) / (# days of diary entry)
- Average number of BMs per week: 7 * (# BMs) / (# days of diary entry)
- Average number of loose stool BMs per week: 7 * (# BMs with Bristol stool scale score of 6 or 7) / (# days of diary entry)

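### SAP 8.2 and 8.3 pick different 14-day windows for an overlong diary, so 3-month responder status can depend on which is followed after a reschedule

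*SAP*

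**What the plan says.** Protocol 2.7 (repeated in SAP 8.2) provides a recovery step. A woman who reaches a 3, 6 or 12 month visit with fewer than 10 completed diary days may move that visit once, by up to a fortnight. In the meantime she keeps a diary, described in these terms: "while completing a new Treatment Diary for the remainder of the required 14 consecutive day diary period". Protocol 3.2 sets the completeness condition for a responder: "An enrolled subject must also have at least 10 out of 14 consecutive days of recorded diary data on her Treatment Diary".

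Three SAP sentences then bear on which days are analysed:

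- SAP 8.2, when more than 14 days of data exist: "data from the first 14 consecutive days which has at least 10 days completed will be analyzed".
- SAP 8.3, on the same situation: "If >14 days were completed for any time period, only the first 14 days will be used for computations".
- SAP 8.3, on repeats: "If a diary was repeated as allowed per protocol or Sponsor-approved Protocol Deviation, the calculations will be performed on the repeat diary information only".

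SAP 8.2 also says that ITT analyses of response "will classify subjects who do not complete the diary (either partially completed, not completed, or discontinued study prior to that time point) as non-responders". SAP 11.1 takes the definition of response from 8.3 and the treatment of missing data from 8.2. It does not rank the two sections.

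**The concern.** The 8.2 window moves forward until it finds 10 completed days. The 8.3 window is fixed at the start and carries no such condition. A woman whose first 14-day diary period was too sparse is the person the reschedule exists for, and she is also the person for whom the two windows differ. The choice between them feeds directly into the primary endpoint.

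The trial is open-label, and SAP 8.4 allows the sponsor to run ad hoc analyses during the study. A derivation rule still open at that stage could be settled with results in view. Nothing suggests that this is intended, but a plan should not leave room for it.

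**Working it through.** **The plan's own figure.** With p0 = 0.40, one-sided alpha 0.025 and N = 40 (SAP 6.2), the smallest rejecting count of the exact binomial test is 23, with exact alpha 0.0189. Power at a 67% response rate is 0.924, so the stated power of at least 90% is reproduced. This point does not affect it.

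**How many days can accumulate.** At most 9 completed days at the first attempt plus 14 in a full new diary gives 9 + 14 = 23, so the over-14-day sentences can apply.

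**Applying each rule to constructed diaries.** These are illustrations, not trial data. Baseline is 10 episodes in 14 days: 7 × 10/14 = 5.0 per week, so response needs 2.5 per week or less. The weekly rate is 7 × episodes / completed days. The new diary is fully completed on days 15–28.

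- Diary A: days 1–8 completed with 8 episodes; new diary has 2 episodes, on days 16 and 20.
- Diary B: days 1–8 completed with 1 episode; new diary has 6 episodes, on days 15–18, 21 and 22.
- Diary C: days 6–14 completed with 6 episodes, on days 6–11; new diary has none.

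| Rule | A | B | C |
|---|---|---|---|
| 8.2: first 14-day run with at least 10 completed | Days 11–24: 7×2/10 = 1.4, 72% reduction, responder | Days 11–24: 7×6/10 = 4.2, 16%, non-responder | Days 2–15: 7×6/10 = 4.2, 16%, non-responder |
| 8.3: first 14 calendar days | 8 completed: incomplete, non-responder | 8 completed: incomplete, non-responder | 9 completed: incomplete, non-responder |
| 8.3: first 14 completed days | 7×10/14 = 5.0, 0%, non-responder | 7×5/14 = 2.5, 50%, responder | 7×6/14 = 3.0, 40%, non-responder |
| 8.3: repeat diary only | 7×2/14 = 1.0, 80%, responder | 7×6/14 = 3.0, 40%, non-responder | 0, 100%, responder |

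Status flips in both directions. In A, 8.2 gives a responder and either reading of the first-14-days sentence does not. In B, 8.2 gives a non-responder, and the first-14-completed-days reading gives a responder at exactly 50%. In C, 8.2 and the repeat rule disagree.

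**Where the rules agree.** A diary of 16 consecutive completed days gives days 1–14 under both over-14-day rules. If days 1–8 are followed only by days 15–20, the total is 8 + 6 = 14. The 8.3 sentence is then not triggered, and no 14-day run reaches 10 completed days. If the first diary was started late and the new one follows without a gap, the first 14 days can be complete and no conflict arises.

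**Weight of one woman.** 1/40 = 2.5 points; 1/150 = 0.7 points. Exact one-sided p-values:

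- N = 40: 23 responders p = 0.0189 (reject); 22 responders p = 0.0392 (do not reject).
- N = 150: 73 responders p = 0.0193 (reject); 72 responders p = 0.0284 (do not reject).

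**The case against.** The best defence is that 8.3 is shorthand for 8.2. Just before its first-14-days sentence, 8.3 limits calculations to completed diaries, with "10+ days for 3, 6, and 12 month diaries as per Section 8.2". On that view a woman with a valid later run has a complete diary, and 8.2, which also holds the ITT non-response rule, would not call her incomplete. This is a fair reading, but the cross-reference covers the threshold and not the window. If completeness is judged by 8.2 and the rate is then taken from the first 14 calendar days, diary A gives 7×8/8 = 7.0 per week (non-responder) and diary B gives 7×1/8 = 0.875 per week, an 82.5% reduction (responder). Both are the opposite of 8.2's result.

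A reader might infer that 8.3 cancels the recovery step for every woman who reschedules. The documents do not support that. The sentence applies only when more than 14 days are completed. If the new diary counts as a repeat allowed by protocol, 8.3 analyses it alone and the recovery works in diary A. Whether it does count is unclear. Protocol 2.7 describes repeats for exceptional circumstances, with Executive Committee approval, separately from the reschedule. It also calls the reschedule diary new while tying it to the remainder of the period. Treating it as a repeat leaves the conflict with 8.2 in diary C.

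A reader might also infer that the primary result is at risk. The documents give no reschedule rate. At the assumed 67% response, the expected counts are 0.67 × 40 = 26.8 against 23 needed and 0.67 × 150 = 100.5 against 73. A changed conclusion is unlikely.

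**Conclusion.** The contradiction between two current SAP sentences is real and bears on the primary endpoint, but it is narrow. On calendar days it needs fewer than 10 completed days in the first 14 together with more than 14 completed overall. In that case 8.3 taken literally turns a woman with a valid later run into an ITT non-responder. The undefined status of the reschedule diary adds a possible third answer.

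How many women this touches cannot be determined from the documents. Each one shifts the reported ITT rate by 2.5 points at 40 subjects or 0.7 points at 150, and alters the test only if the count sits at the rejection boundary. The flips shown rest on constructed diaries: they prove that the rules can disagree, not how often they will. This is a minor correction, worth making because it is cheap and removes a choice that could otherwise be made after the data are seen.

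**What to change.** Replace the first-14-days sentence in SAP 8.3 with one window rule, and align or delete the competing wording in 8.2. The rule would be the first 14 consecutive days that meet that diary's own completeness threshold: 12 of 14 for the Baseline and Test Diaries, 10 of 14 for the 3, 6 and 12 month Treatment Diaries. Simply sending every diary to the present 8.2 rule would not do, because its 10-day condition would then apply to diaries that need 12 days, including the baseline that is the denominator of the endpoint.

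State also, before database lock, whether the reschedule diary replaces or extends the first one, and so whether a window may straddle both.

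The cost is a one- or two-sentence SAP edit. Sample size, power and data collection are unchanged.
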